7.3. Body Weight, Height, and Vital Signs

Descriptive statistics will be provided for body weight, BMI, and vital signs as follows:

- Baseline value
- Value at each postbaseline time point [visit]
- Change from baseline at each postbaseline time point [visit]

A baseline value will be defined as the last available value collected on or prior to the date of first dose of study drug. Change from baseline to a postbaseline visit will be defined as the postbaseline value minus the baseline value.

In the case of multiple values in an analysis window, data will be selected for analysis as described in Section 3.8.3. No formal statistical testing is planned.

A by-participant listing of vital signs will be provided by participant ID number and visit in chronological order. Body weight, height, and BMI will be included in the vital signs listing if space permits. If not, they will be provided separately.

7.4. Prior and Concomitant Medications and Disease Specific Medications

Prior and concomitant medications (ie, non-antiretroviral [non-ARV] medications) collected at screening and during the study will be coded using the current version of the World Health Organization (WHO) Drug Dictionary.

Disease-specific medications (ie, nonstudy drug ARV) used prior to, during, or after the study (if collected) will be coded using the Gilead-modified WHO Drug Dictionary.

7.4.1. Prior and Disease-Specific Prior Medications

Prior and disease-specific prior medications are defined as any medications taken before a participant took their first dose of study drug.

A summary of prior or disease-specific prior medications will not be provided.

7.4.2. Concomitant Medications

Concomitant medications are defined as medications taken on or after first dose date of study drug. Use of concomitant medications will be summarized by preferred name using the number and percentage of participants for GS-6212 cohort. A participant reporting the same medication more than once will be counted only once when calculating the number and percentage of participants who received that medication. The summary will be ordered by preferred term in descending overall frequency. For drugs with the same frequency, sorting will be done alphabetically.

For the purposes of analysis, any medications with a start date prior to or on the first dosing date of study drug that continued to be taken after the first dosing date, or medications started after the first dosing date of study drug will be considered to be concomitant medications. Medications started and stopped on the same day as the first dosing date of study drug will also be considered concomitant. Medications with a stop date prior to the date of first dosing date of study drug will be excluded from the concomitant medication summary. If a partial stop date is entered, any medication with the month and year (if day is missing) or year (if day and month are missing) prior to the date of first study drug administration will be excluded from the concomitant medication summary. If a partial start date is entered, any medication with the month and year (if day is missing) or year (if day and month are missing) on or after the study drug start date will be included in the concomitant medication summary. Medications with completely missing start and stop dates will be included in the concomitant medication summary, unless otherwise specified. Summaries will be based on the Safety Analysis Set. No formal statistical testing is planned.

All prior and concomitant medications (other than per-protocol study drugs) and all nonstudy drug ARV medications will be provided in by-participant listings sorted by participant ID number and administration date in chronological order.

7.5. Electrocardiogram Results

Summaries of investigator assessment of ECG readings will be provided for the Safety Analysis Set for each scheduled visit. No formal statistical testing is planned.

7.5.1. Investigator Electrocardiogram Assessment

A shift table of the investigators' assessment of ECG results at each visit compared with baseline values will be presented using the following categories: normal; abnormal, not clinically significant; abnormal, clinically significant; or missing. If all participants have a baseline value then no missing category will be presented at baseline. The number and percentage of participants in each cross-classification group of the shift table will be presented. Participants with a missing value at baseline or postbaseline will not be included in the denominator for percentage calculation.

No formal statistical testing is planned.

A by-participant listing for ECG assessment results will be provided by participant ID number and visit in chronological order.

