3.8.2. Analysis Visit Windows

Participant visits might not occur on protocol-specified days. Therefore, for the purpose of analysis, observations will be assigned to analysis windows.

The analysis windows for HIV-1 RNA are provided in Table 3-1; for hematology, chemistry, urinalysis, and eGFR_{CG} in Table 3-2; for vital signs and weight in Table 3-3; for ECGs and coagulation in Table 3-4; and CD4 cell count and percentage in Table 3-5.

Table 3-1. Analysis Visit Windows for HIV-1 RNA

		Visit Window Study Day	
Nominal Visit	Nominal Study Day	Lower Limit	Upper Limit
Baseline	1	(none)	1
Day 2	2	2	2
Day 3	3	3	3
Day 4	4	4	5
Day 7	7	6	7
Day 8	8	8	8
Day 9	9	9	9
Day 10	10	10	10
Day 11	11	11	11
Day 25	25	12	(none)

Cohort GS-6212 will be compared to the historical placebo control group through Study Day 11.

The percentage of participants with HIV-1 RNA < 50 copies/mL will be displayed on Day 11 (last value prior to starting standard of care) and on Days 25.

Table 3-2. Analysis Visit Windows for Hematology, Chemistry (including Thyrotropin), Urinalysis and $eGFR_{CG}$

		Visit Window Study Day	
Nominal Visit	Nominal Study Day	Lower Limit	Upper Limit
Baseline	1	(none)	1
Day 3	3	2	5
Day 7	7	6	9
Day 11	11	10	11
Day 25	25	12	(none)

Table 3-3. Analysis Visit Windows for Vital Signs and Weight

		Visit Window Study Day	
Nominal Visit	Nominal Study Day	Lower Limit	Upper Limit
Baseline	1	(none)	1
Day 2*	2	2	2
Day 3	3	3	3
Day 4*	4	4	5
Day 7	7	6	9
Day 11	11	10	11
Day 25	25	12	(none)

^{*}Weight is not scheduled to be collected on Day 2 and Day 4 per protocol, so any weight collected on Day 2 will be considered for Day 3, any weight collected during Day 4 period will be considered for Day 7.

Table 3-4. Analysis Visit Windows for ECGs and Coagulation Tests

		Visit Window Study Day	
Nominal Visit	Nominal Study Day	Lower Limit	Upper Limit
Baseline	1	(none)	1
Day 7	7	2	9
Day 11	11	10	11
Day 25	25	12	(none)

		Visit Window Study Day	
Nominal Visit	Nominal Study Day	Lower Limit	Upper Limit
Baseline	1	(none)	1
Day 11	11	2	11
Day 25	25	12	(none)

Table 3-5. Analysis Visit Windows for CD4 Cell Count and Percentage

3.8.3. Selection of Data in the Event of Multiple Records in an Analysis Visit Window

Depending on the statistical analysis method, single values may be required for each analysis window. For example, change from baseline by visit usually requires a single value.

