If multiple valid, nonmissing measurements exist in an analysis window, records will be chosen based on the following rules if a single value is needed:

- For baseline, the last nonmissing value on or prior to the first dose of study drug will be selected, unless specified differently. If there are multiple records with the same time or no time recorded on the same day, the baseline value will be the average of the measurements for continuous data (except for HIV-1 RNA, see below), or the measurement with the lowest severity (ie, normal will be selected over abnormal for safety ECG findings) for categorical data.
- For postbaseline values:
 - The record closest to the nominal day for that visit will be selected (with the exception of CD4+ cell count and CD4% in which the latest record will be selected and HIV-1 RNA level [see below]).
 - If there are 2 records that are equidistant from the nominal day, the later record will be selected.
 - If there is more than 1 record on the selected day, the average will be taken for continuous data (except for HIV-1 RNA, see below) and the worst severity will be taken for categorical data, unless otherwise specified.
- For baseline and postbaseline HIV-1 RNA, the latest (considering both date and time) record(s) in the window will be selected. If both "Roche COBAS 6800" and "Roche COBAS 6800 Repeat" (ie, the HIV-1 RNA result obtained from an additional aliquot of the original sample) are available with the same collection time, the results from the "Roche COBAS 6800 Repeat" will be selected for analysis purposes; otherwise, if there are multiple "Roche COBAS 6800" records with the same collection time, the geometric mean will be taken for analysis purposes.

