7.2.2.2. Summaries of Laboratory Abnormalities

Laboratory data that are categorical will be summarized using the number and percentage of participants in the study with the given response at baseline and each scheduled postbaseline visit.

The following summaries (number and percentage of participants) for treatment-emergent laboratory abnormalities will be provided by lab test; participants will be categorized according to the most severe postbaseline abnormality grade for a given lab test:

- Graded laboratory abnormalities
- Graded laboratory abnormalities collected up to Study Day 11 (prior to the participant initiating standard of care therapy on Day 11)
- Grade 3 or 4 laboratory abnormalities

For all summaries of laboratory abnormalities, the denominator is the number of participants with ≥ 1 nonmissing postbaseline value.

A by-participant listing of treatment-emergent laboratory abnormalities and a listing of treatment-emergent Grade 3 or 4 laboratory abnormalities will be provided by participant ID number and visit in chronological order. These listings will include all test results that were collected throughout the study for the lab test of interest, with all applicable severity grades and abnormal flags displayed.

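### The only ECG table takes one record per visit window, so a clinically significant unscheduled or early-termination ECG can be left out; add a worst post-baseline row

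*SAP*

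**What the plan says.** SAP Section 7.5 limits the ECG tabulation to planned visits: "Summaries of investigator assessment of ECG readings will be provided for the Safety Analysis Set for each scheduled visit". Section 7.5.1 gives its form, a shift table in which "ECG results at each visit compared with baseline values will be presented using the following categories". The same section adds a chronological by-participant listing. No other ECG table is planned.

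The windows are in Section 3.8.2 ("Table 3-4. Analysis Visit Windows for ECGs and Coagulation Tests"). The Day 7 window covers Study Days 2 to 9, the Day 11 window covers Days 10 and 11, and the Day 25 window starts on Day 12 and has no upper limit.

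Section 3.8.3 chooses among several post-baseline records in one window: "The record closest to the nominal day for that visit will be selected". The exceptions are CD4 and HIV-1 RNA; ECG is not one of them. For ties, "If there are 2 records that are equidistant from the nominal day, the later record will be selected". The worst category is used only when several records fall on the selected day.

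For graded laboratory abnormalities, Section 7.2.2.2 has a different rule: "participants will be categorized according to the most severe postbaseline abnormality grade for a given lab test". It gives this for the whole study and for the period up to Study Day 11.

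**The concern.** A by-visit table built from the nearest record shows each participant's status near Days 7, 11 and 25. It does not show whether a participant ever had a clinically significant ECG after starting GS-6212. The closest-day step comes before the worst-severity step, so the protection offered by the latter does not reach across the window.

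Safety and tolerability is a secondary objective (Section 1.1). A reader who relies on the shift table could conclude that nobody moved to abnormal and clinically significant when the listing shows that someone did. Unscheduled ECGs are not the only source. Appendix 1 requires an ECG at early termination, and the rule can set that record aside for a participant who stopped early.

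**Working it through.** The SAP states no figure on this point to reproduce, so the check applies its selection rule to its own windows.

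**Inputs**
- Scheduled post-baseline ECGs: Days 7, 11 and 25, plus the early-termination visit (Appendix 1). The early-termination visit takes place within 72 hours of stopping (footnote c). The Day 25 visit may move by 2 days either way.
- Windows: Table 3-4, as above.
- Selection: Section 3.8.3. Section 7.5.1 does not cross-refer to it, as Sections 7.2.1 and 7.3 do. But Section 3.8.3 is general, names ECG findings in its baseline rule, and is the only rule for records placed in the Table 3-4 windows.

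**Rule.** Let a normal ECG fall on day s, a clinically significant ECG on day u of the same window, and let N be the nominal day. The significant ECG is tabulated only if
- |u − N| < |s − N|, or
- |u − N| = |s − N| and u > s (the later record wins a tie), or
- u = s (the worst reading on the same day).

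**Results**

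| Window | Day of normal ECG | Significant ECG tabulated on | Significant ECG left out on |
|---|---|---|---|
| Day 7 (Days 2–9) | 7 | 7 | 2–6, 8, 9 |
| Day 11 (Days 10–11) | 11 | 11 | 10 |
| Day 25 (Day 12 on) | 25 | 25 | 12–24, and 26 on |
| Day 25 (Day 12 on) | 23 | 23–27 | 12–22, and 28 on |
| Day 25 (Day 12 on) | 27 | 24–27 | 12–23, and 28 on |

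The Day 7 window holds 9 − 2 + 1 = 8 days, and on 8 − 1 = 7 of them the record loses. This counts days; it is not a probability of loss.

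**Early-termination case.** A participant has a normal ECG on Day 7, stops that day, and has the early-termination ECG on Day 8 or 9, inside the 72 hours. Its distance from the nominal day is 1 or 2, against 0 for the Day 7 record, so it is not tabulated. On Day 10 it would fall in the Day 11 window and would count if no Day 11 ECG followed.

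**When nothing is lost.** An ECG that is the only record in its window, or the nearest to the nominal day, is counted. So is one on the same day as the selected record.

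**Scale.** In a cohort of 6 to 8 (Section 1.3), one participant is 1/8 = 12.5% to 1/6 = 16.7%. This shows only what one assumed event would weigh.

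**After the fix.** The worst category over all ECGs after first dose retains every record in the right-hand column.

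**The case against.** The strongest reply is that the SAP does what it says. Section 7.5 promises summaries at scheduled visits, and Section 7.5.1 delivers a by-visit table. Numeric laboratory results and vital signs follow the same single-record rule. In Section 7.2.2.2 the worst-grade rule applies to graded abnormalities, while categorical laboratory data, arguably the nearer analogue of an ECG category, are also summarized by scheduled visit. This stands: the ECG table follows the by-visit convention, and the SAP does not contradict itself here.

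A reader might infer that the rule favours GS-6212. The document does not support that. The rule ignores the reading: if the Day 7 ECG is clinically significant and a repeat on Day 8 is normal, the abnormal record is kept. Whether unscheduled ECGs are mostly prompted by symptoms or are mostly repeats cannot be known from the SAP.

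A reader might also infer that the finding disappears from the report. It does not. It stays in the ECG listing, which is easy to read for one small cohort, and it enters the adverse event tables of Section 7.1.7.1 if reported as an event. The SAP does not say whether it must be; that may be settled in the protocol, which is not at hand.

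Nor can 12.5% to 16.7% be called a hidden incidence. The by-visit table reports no cumulative incidence, and the event is assumed.

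What remains is that no table answers the question of any clinically significant ECG after first dose. A listing does not fully replace one: Section 7.2.2.2 lists laboratory abnormalities and still tabulates the worst grade.

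**Conclusion.** The point holds as a minor to moderate gap in the safety summary. In the Day 7 and Day 25 windows, a clinically significant ECG is left out of the only ECG table when another record lies nearer the nominal day, which is the usual position once the scheduled ECG has been done. The two-day Day 11 window adds only Day 10.

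This rests on two assumptions: that Section 3.8.3 governs ECGs, which its wording and Table 3-4 support, and that at least one participant has a second ECG in a window. If nobody does, the table loses nothing. Efficacy conclusions are unaffected, and no ECG testing is planned. Bias in favour of the drug is not shown.

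**What to change.** Keep the by-visit rows. In Section 7.5.1, add a worst post-baseline row to the shift table, defined as the most severe investigator assessment among all scheduled, unscheduled and early-termination ECGs after first dose. Show it for the period before standard of care starts and for the whole study, in line with the most-severe-grade summaries in Section 7.2.2.2. If the SAP is already final, Section 1 provides for documenting the change in the clinical study report.

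The cost is one sentence and one or two table rows from data already collected. The downside is that counts of ECG abnormalities may look slightly less favourable than in the by-visit rows.

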7.6. Other Safety Measures

A by-participant listing of subject pregnancies during the study will be provided by participant ID number if applicable. No additional safety measures are specified in the protocol.

Although not necessarily related to safety, a by-participant listing of all comments received during the study on the comments eCRF will be provided by participant ID number, and eCRF form for which the comment applies.

7.7. Changes From Protocol-Specified Safety Analyses

There are no deviations from the protocol-specified safety analyses.

8. PHARMACOKINETIC (PK) ANALYSES

8.1. PK Sample Collection and Analyses

Intensive PK samples are planned to be collected on Study Day 1 and Day 10 at the following timepoints for all cohorts (as applicable): predose (≤ 30 minutes before dose), 0.25, 0.5, 1, 2, 3, 4, 6, 8, and 12 hours postdose (12 hour postdose sample is optional) on respective days of dosing. Additionally, single trough PK samples will be drawn prior to AM drug dosing on Study Days 2, 3, 4, 7, 8, 9, and 11. Concentrations of GS-6212 in plasma will be determined using validated bioanalytical assays.

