AUC area under the plasma/serum concentration versus time curve

AUC_{0-t} partial area under the concentration versus time curve from time "0" to time "t"

AUC_{last} area under the concentration versus time curve from time zero to the last quantifiable

concentration

AUC_{tau} area under the concentration versus time curve over the dosing interval AUC_{inf} area under the concentration versus time curve from time zero to infinity

C_{last} last observed quantifiable concentration of the drug

C_{max} maximum observed concentration of drug

C_t concentration at time t

C_{tau} observed drug concentration at the end of the dosing interval

C_{trough} concentration at the end of the dosing interval

CL/F apparent oral clearance after administration of the drug:

 $CL/F = Dose/AUC_{inf}$, where "Dose" is the dose of the drug

 T_{last} time (observed time point) of C_{last} T_{max} time (observed time point) of C_{max}

 $t_{1/2}$ estimate of the terminal elimination half-life of the drug, calculated by dividing the natural log of

2 by the terminal elimination rate constant (λ_z)

 V_z/F apparent volume of distribution of the drug

 λ_z terminal elimination rate constant, estimated by linear regression of the terminal elimination

phase of the concentration of drug versus time curve

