8.1.2. PK Parameters

PK parameters will be generated for all participants for whom parameters can be derived in the PK Analysis Set. The analyte presented in Table 8-1 will be evaluated if data are available.

Table 8-1. Study Treatments and Associated Analyte

GS-6212 Cohort	Treatment	Analyte
All GS-6212 Cohorts	GS-6212	GS-6212

The analyte and parameters presented in Table 8-2 will be used to evaluate the PK objectives of the study, as appropriate. The PK parameters to be estimated in this study are listed and defined in the PK Abbreviations section.

Table 8-2. PK Parameters for Each Analyte

Analyte	Parameters
GS-6212	For intensive PK sampling up to 12 hours postdose on Day 1 and Day 10, following parameters will be calculated (as applicable): AUC _{0-t} , AUC _{last} , AUC _{tau} , C _{max} , C _t , C _{last} , C _{tau} , C _{avg} , T _{max} , T _{last} , and additionally λ_z , CL/F, t _{1/2} , and V _z /F if applicable; accumulation ratio (Day 10 / Day 1) for Ct, C _{max} , AUC _{0-t} , and AUC _{last} ; C _{trough} on Day 11; C _{trough,avg} (average C _{trough} based on all predose trough sampling done across several days- D2, D3, D4, D7, D8, D9, D10, and D11)

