8.2.2. PK Analyses

Individual PK parameter data listings and summaries will include all participants for whom PK parameter(s) can be derived. The sample size for each PK parameter will be based on the number of participants with nonmissing data for that PK parameter. Data and summary statistics will be presented to three significant digits.

The following tables will be provided for GS-6212:

- Individual estimates and summary statistics of plasma pharmacokinetic parameters on Day 1 and Day 10
- Individual data and summary statistics of plasma concentration (ng/mL) at protocol-specified sampling times
- Statistical comparisons of plasma pharmacokinetic parameter estimates on Day 10 vs Day 1 for the accumulation analysis

Accumulation analysis of analyte GS-6212 will be evaluated by comparing the relevant Day 10 PK parameters to Day 1 PK parameters within cohort 1. The analytes and parameters are presented in Table 8-3.

A mixed effects model with the natural log-transformed PK parameter as the dependent variable, a fixed effect for day, and a random effect for participant, will be used to estimate the difference between Day 10 and Day 1. A 90% CI for the true difference on the log-scale across all participants will be estimated. The estimate and associated 90% CI will be exponentiated to obtain an estimate of the GLSM ratio and its associated 90% CI.

The following SAS® PROC MIXED code will provide assessment for accumulation ratio for natural-log transformed parameters.

```
proc mixed;
where analyte='GS-6212 and paramed='parameter';
class subjid day;
random subjid;
model lnest = day / ddfm=kr;
lsmeans day / diff cl alpha = 0.1;
estimate 'Test (Day 10) versus Reference (Day 1)' day -1 1 / cl alpha = 0.10;
ods output Estimates = LS_Diffs LSMeans = LS_Means CovParms = MSE;
run;
```

Table 8-3. Analytes and PK Parameters for Estimation of Accumulation Ratios

Analytes	PK Parameters on Day 1	PK Parameters on Day 10
GS-6212	AUC _{0-8h} , AUC _{last} , C _{8h} , C _{max}	AUC _{0-8h} , AUC _{last} , C _{8h} , C _{max}

The following figures will be provided for GS-6212:

- Mean $(\pm SD)$ concentration data on Day 1 (on linear and semilogarithmic scales).
- Mean (± SD) concentration data on Day 10 (on linear and semilogarithmic scales).

• Mean (± SD) concentration data from Day 1 through Day 11 (on linear and semilogarithmic scales).

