- f See detailed list of laboratory assessments in Section 6.3.7 of the master protocol.
- Participants who meet the criteria for virologic failure at Day 11 will be tested for the potential development of resistance against all components of the treatment regimen, including the study drug. See Section 6.3.9.1.3 of the master protocol for management of virologic failure.
- h Participants assigned female at birth and of childbearing potential only.
- i A negative urine pregnancy test is required prior to study drug dosing on Day 1. Positive urine pregnancy tests will be confirmed with a serum test.
- j A serum FSH test is required for participants assigned female at birth who are younger than 54 years, not on hormonal contraception, and who have stopped menstruating for ≥ 12 months but do not have documentation of ovarian hormonal failure.
- k Intensive PK samples should be collected at these time points for all cohorts (relative to AM dosing): predose (\$\leq\$ 30 minutes before dose), 0.25, 0.5, 1, 2, 3, 4, 6, 8, and 12 hours postdose (\$\leq\$ 1 and 10). Please note that the 12-hour postdose sample (if collected) on Days 1 and 10 should be sampled prior to the administration of the PM dose, as applicable.
- 1 Single trough PK sample should be drawn prior to AM drug dosing (as applicable) on the indicated dosing days (ie, Days 2, 3, 4, 7, 8, 9, and 11).
- m From the time of obtaining informed consent through the first administration of study drug, record all SAEs, as well as any nonserious AEs related to protocol-mandated procedures, on the AE eCRF. All other untoward medical occurrences observed during the screening period, including exacerbation or changes in medical history are to be captured on the medical history eCRF. See Section 7, Adverse Events and Toxicity Management, for additional details.
- n Study drug bottles of GS-6212 will be dispensed on Day 1 (see Section 5.2.4).
- o For Cohort 1, a 100-mg dose of GS-6212 will be administered twice daily (ie, once every 12 hours ± 1 hour) on Days 1 through 10 (for further details on dosing and meal requirements, see Section 5.2.4). Subsequent cohort doses, dosing regimens, meal requirements (fasted or fed), and progression between cohorts will be adaptive and determined as summarized in Section 3.1.1.
- p Participants will take their study drug doses at home on Days 5 and 6.

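### The Day 10/Day 1 accumulation ratio for AUClast has no common end time, so it can mix 0-8 h and 0-12 h areas when the optional 12-hour sample is missing on one day

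*SAP*

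**What the plan says.** - **Sampling.** SAP Section 8.1 lists intensive samples on Days 1 and 10 from predose to "12 hours postdose (12 hour postdose sample is optional) on respective days of dosing". Footnote k of the study procedures table (Appendix 1) also treats the last draw as conditional: the "12-hour postdose sample (if collected) on Days 1 and 10 should be sampled prior to the administration of the PM dose". The last assured sample is therefore at 8 h.
- **Definition.** The pharmacokinetic abbreviations define AUClast as the "area under the concentration versus time curve from time zero to the last quantifiable" concentration. Its upper limit is whatever Tlast is on that day.
- **BLQ values.** Section 8.1.1 treats BLQ samples after the first quantifiable concentration as missing. A 12-hour sample that is drawn but BLQ therefore also leaves the area ending at 8 h or earlier.
- **Accumulation analysis.** Section 8.2.2 states: "Accumulation analysis of analyte GS-6212 will be evaluated by comparing the relevant Day 10 PK parameters to Day 1 PK parameters within cohort 1". Table 8-3 names four parameters for both days: AUC0-8h, AUClast, C8h and Cmax. Table 8-2 also lists AUClast among the accumulation ratios.
- **Model.** The log-transformed parameter is fitted with "a fixed effect for day, and a random effect for participant". On precision: "A 90% CI for the true difference on the log-scale across all participants will be estimated". The estimate and interval are then exponentiated to a ratio of geometric least-squares means.

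No section requires the same Tlast on both days, truncates AUClast to a shared time, or sets aside participants whose Tlast differs.

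**The concern.** An accumulation ratio is meant to compare exposure over the same part of the dosing interval after the first dose and after repeated dosing. AUC0-8h does this. AUClast does so only if Tlast is the same on both days for each participant, and the optional 12-hour draw gives an ordinary way for it not to be.

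If Day 10 runs to 12 h and Day 1 stops at 8 h, four extra hours of area enter the numerator and the ratio is too high. In the reverse case it is too low. The AUClast and AUC0-8h ratios would then disagree in the same table for a reason unrelated to drug disposition, and the SAP does not say which of the two to read. With 6 to 8 participants planned per cohort (Section 1.3), a single unequal pair carries visible weight.

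**Working it through.** The SAP gives no figure for this point, so there is none to reproduce.

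**Inputs from the SAP:** last assured sample 8 h and optional sample 12 h (Section 8.1); cohort size 6 to 8 (Section 1.3); dosing every 12 hours in Cohort 1 (Appendix 1, footnote o); linear-up/log-down AUC (Section 8.1.1).

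**Assumed:** the half-life h, because the SAP gives none. The range shown is 3 to 24 h.

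**Step 1: one participant.** For a one-compartment decline, the share of the 0-12 h area that lies in 0-8 h is

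f = (1 − 2^(−8/h)) / (1 − 2^(−12/h)).

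If only Day 1 has the 12-hour sample, the AUClast ratio is f times the ratio from matched windows. If only Day 10 has it, the factor is 1/f.

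**Step 2: the cohort.** With both days present for everyone, the model's day difference is the mean of the within-participant log differences. One unequal pair among n multiplies the cohort ratio by f^(1/n) or (1/f)^(1/n).

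| Half-life (assumed) | f | 1/f | f^(1/6) | (1/f)^(1/6) |
|---|---|---|---|---|
| 3 h | 0.899 | 1.11 | 0.982 | 1.018 |
| 6 h | 0.804 | 1.24 | 0.964 | 1.037 |
| 12 h | 0.740 | 1.35 | 0.951 | 1.051 |
| 24 h | 0.704 | 1.42 | 0.943 | 1.060 |

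One unequal pair in six therefore moves the cohort ratio by about 2% to 6%. With eight participants the range is about 1.3% (0.899^(1/8) = 0.987) to 4.5% ((1/0.704)^(1/8) = 1.045).

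**Step 3: a fuller profile.** I added absorption (assumed rate 1.5/h), used the SAP's sampling times and AUC rule, and took the Day 10 morning dose as the 19th 12-hourly dose. For half-lives of 2 to 24 h, a participant's ratio relative to the matched 0-12 h ratio is

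- 1.07 to 1.47 times too high if only Day 10 has the 12-hour sample;
- 0.94 to 0.70 of its proper value if only Day 1 has it.

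At a 12 h half-life, the matched ratios are 2.12 (0-8 h) and 2.09 (0-12 h). The unequal pairs give 2.91 or 1.52. Two of six unequal in the same direction move the cohort ratio by about +2% to +14% or −2% to −11%.

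**Step 4: does a common window remove the effect?** Yes. The matched 0-8 h and 0-12 h ratios are 1.17 and 1.17 (half-life 4 h), 1.62 and 1.60 (8 h), 2.12 and 2.09 (12 h), and 3.67 and 3.59 (24 h). The choice of window hardly matters, provided it is the same on both days.

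**The case against.** The strongest reply is that the SAP already holds the remedy. AUC0-8h, C8h and Cmax sit beside AUClast in Table 8-3 and do not depend on the optional draw, so an unaffected exposure ratio will be reported in any case. Tlast is itself a Table 8-2 parameter and individual parameters are listed, so an unequal pair could be seen. Section 8.1.1 leaves AUC calculation to the PK scientist, and Section 8.3 allows a sensitivity analysis that excludes questionable data.

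Most of this stands, and it limits the consequence. It does not close the gap. The allowance for nominal times in Section 8.1.1 concerns AUC over specific intervals, which AUClast is not. Section 8.3 is discretionary and triggered by questionable data, and a valid 12-hour sample is not questionable.

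The size is also modest against the precision available. If the within-participant log SD were 0.15 to 0.30 (assumed), a 90% CI from six pairs would have a half-width of 2.015 × SD × √(2/6) on the log scale, a factor of about 1.19 to 1.42 either way. A shift of 2% to 6% lies well inside that.

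A reader might infer three stronger things that the document does not support:

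- **That the AUClast ratio is biased.** It can be, but only where Tlast differs within a participant. The SAP gives no collection rate for the 12-hour sample, and unequal pairs in opposite directions partly cancel and mainly widen the interval.
- **That the cohort ratio could be off by 10% to 42%.** That needs every participant to be unequal in the same direction, and nothing in the SAP suggests it.
- **That accumulation is formally tested.** The SAP estimates a ratio with a 90% CI and states no hypothesis or acceptance bound.

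**Conclusion.** The point holds as a gap in specification. As written, the SAP allows the AUClast accumulation ratio to compare areas of different length within a participant, through the optional 12-hour sample or through late BLQ values. For an uncollected 12-hour sample and assumed half-lives of 3 to 24 h, an affected participant's ratio is off by a factor of about 0.70 to 0.90 or 1.11 to 1.42. One such participant in six moves the cohort ratio by about 2% to 6%. Where Tlast agrees on both days for every participant, the distortion is nil.

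The consequence is small. This is one descriptive PK parameter with an unaffected companion in the same table. Cohorts 2 to 5 were not enrolled (Section 2.2), so the ratio guides no later cohort here. Section 8.2.3 plans no formal PK/PD analysis, and no efficacy or safety conclusion depends on it.

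**What to change.** Either of two changes is enough:

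1. Remove AUClast from the accumulation ratios in Tables 8-2 and 8-3 and rely on AUC0-8h, which is already planned. AUClast can stay as a descriptive parameter for each day.
2. Keep it, but state that for the ratio each participant's area is computed to the last nominal time quantifiable on both Day 1 and Day 10, which means no later than 8 h if either 12-hour sample is missing. This also covers late BLQ values.

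The cost is wording only, with no new data. Section 1 already provides for changes after SAP finalization to be documented in the CSR. The downside is one fewer accumulation parameter under the first option, or a truncated one under the second, which for many participants may coincide with AUC0-8h.
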